1.0 TRIAL SUMMARY

Abbreviated Title	PCR-MIB Pembrolizumab with ChemoRadiotherapy for Muscle Invasive Bladder cancer
Trial Phase	Phase II
Clinical Indication	Patients with nonmetastatic, muscle invasive bladder cancer who either wish to attempt bladder preservation therapy or are ineligible for cystectomy.
Trial Type	Pilot single arm study: Non-randomized cohort of pembrolizumab with chemoradiotherapy
Type of control	No control arm/placebo
Route of administration	Radiation: 64Gy of radiation therapy in 32 fractions over 6 weeks and 2 days. Chemotherapy (concurrent with radiation): IV concurrent weekly cisplatin 35mg/m ² (6 weeks) Pembrolizumab: IV 200mg 3 weekly commenced concurrently with chemoradiotherapy, and continuing until 12-week cystoscopy
Trial Blinding	Nil
Treatment Groups	30 patients, treated with pembrolizumab and chemoradiotherapy
Number of trial participants	30 patients
Estimated enrolment period	2 years; 5 sites
Estimated duration of trial	2 years of accrual + 3 years follow up
Duration of Participation	19 weeks of study visits; then end of treatment and follow up visits
Objectives	
Primary: To demonstrate that the addition of pembrolizumab to chemoradiotherapy for muscle invasive bladder cancer is feasible as measured by a satisfactorily low rate of unacceptable toxicity.
 
Secondary:
 
 1. To evaluate the efficacy of the addition of pembrolizumab to concurrent chemoradiation regimen using the best response achieved, as assessed by cystoscopy at weeks 19 and 31 of the trial (12 and 24 weeks post completion of chemoradiotherapy). 2. To characterize:

	
a. overall survival (OS); b. metastatic disease-free survival (DMFS); and c. locoregional progression free survival (LRPFS).
 
Exploratory: To evaluate tumour histopathological, molecular genetics, and immunological parameters and their relationship with response to chemoradiotherapy and pembrolizumab.

--	--

2.0 TRIAL DESIGN

This pilot study will enroll patients with maximally resected (via transurethral resection (TURBT) non-metastatic muscle invasive bladder cancer, who either wish to attempt bladder preservation therapy or are ineligible for cystectomy. Patients must have adequate organ function and performance status to receive cisplatin based chemoradiotherapy, and no contraindications to the use of pembrolizumab. The study will enroll 30 patients to be treated with pembrolizumab and chemoradiotherapy.

[figure not shown]
All patients will be planned to be treated with 64Gy of radiation therapy in 32 fractions over 6 weeks and 2 days. All patients will receive cisplatin 35mg/m² IV concurrently weekly with radiation therapy for 6 doses total. Pembrolizumab will commence concurrently with radiation and be given 200mg IV every 21 days, continuing until the 12week cystoscopy and assessment.

Surveillance cystoscopy will be performed 12 weeks after the commencement of chemoradiotherapy, and assess the rate of complete response to therapy. End of treatment and post treatment review visits will occur 4 (i.e. week 19) and 12 (i.e. week 31) weeks post cystoscopy. After the week 31 post treatment visit, patients will enter follow up with clinical assessment, cystoscopy and CT staging performed at intervals until close of study.

The objective of the study is to assess the safety and feasibility of combining pembrolizumab with chemoradiotherapy. The primary endpoint assessed will be safety, as defined by a satisfactorily low rate of unacceptable toxicity (G3-4 adverse events or failure of completion of planned chemotherapy and radiotherapy according to defined parameters). The secondary endpoint will be efficacy, as assessed by the proportion of patients achieving a best response of complete response, considering the first two post chemoradiotherapy cystoscopic assessments, at 19 and 31 weeks. Exploratory analysis will include assessment of tumour histopathological, molecular, genetic and immunological parameters.

It is expected that it will take two years to accrue the required 30 patients.

Figure 1: Study Flow Chart and Key Assessments

	Prestudy Assessments		Chemoradiotherapy		Pembrolizumab Adjvant Period		End of Treatment		Post Treatment Review		Follow Up			
	Week												To be completed 28 days after ceasing treatment at any time and for any reason.	
	Within 6 weeks	1	2	3	4	5	6	7	10	13	16	19	23	
Clinical Assessment		X	X	X	X	X	X	X	X	X	X	X	X	X
Cisplatin		X	X	X	X	X	X							
Radiotherapy		X	X	X	X	X	X	X [^]						
Pembrolizumab		X			X			X	X	X	X	X		
TURBT	X													
Cystoscopy	X										X		X	X
Urine Cytology		X									X		X	X
CT C/A/P	X										X		X	X

*Patients in follow up receive clinical assessment 3 monthly for 12 months, 6 monthly for 18 months, and 12 monthly thereafter for a minimum of 3 years or until death. Cystoscopy and CT C/A/P is performed within 28 days of each of these clinical assessments.

[^] Week 7 pembrolizumab dose will occur in same week as last 2 days of radiotherapy.

PCR-MIB ANZUP1502 Protocol version 5.0; dated: 03 January 2018

3.0 OBJECTIVES, HYPOTHESES & ENDPOINTS

3.1 Primary Objective, Hypothesis & Endpoints

Objective: To demonstrate that the addition of pembrolizumab to chemoradiotherapy for muscle invasive bladder cancer is feasible as measured by a satisfactorily low rate of unacceptable toxicity.

Hypothesis: Pembrolizumab in combination with chemoradiotherapy will be safe and well tolerated in patients with previously untreated muscle invasive bladder cancer.

Endpoints: Occurrence of an unacceptable toxicity affecting patients where an unacceptable toxicity is defined by any of the following:

- a) Occurrence of a grade 3 or 4 acute toxicity (excluding grade 3 or 4 urinary toxicity), occurring either during treatment or within 12 weeks after scheduled completion of treatment, or
- b) Cisplatin being withheld for \geq 2 doses
- c) Cisplatin doses being withheld or reduced such that <66% of the intended total cisplatin dose is delivered
- d) Radiation treatment being delayed beyond more than 7 weeks
- e) Any single pembrolizumab dose being delayed for more than 6 weeks. (Multiple dose delays will not be aggregated).

3.2 Secondary Objectives, Hypothesis & Endpoint

Objectives:

- (1) To evaluate the efficacy of the addition of pembrolizumab to concurrent chemoradiation regimen by estimating the complete response rate (see below).
- (2) To characterize:
 - a. overall survival (OS);
 - b. metastatic disease-free survival (MDFS); and
 - c. locoregional progression free survival (LRPFS).

Hypothesis: The addition of pembrolizumab will improve the efficacy of chemoradiation in patients with bladder cancer.

Endpoints:

- (1) Best response, defined as the better of the responses achieved at either the 1st or 2nd cystoscopic examination after completing therapy. (The 1st and 2nd cystoscopic

examinations take place during weeks 19 and 31 respectively of the trial.) See section 7.1.2.6.2 for definitions of the response levels.

(2) Dates of

- i) death,
- ii) detection of metastatic disease,
- iii) detection of locoregional progression,
- iv) any initiation of any new non-protocol anti-cancer therapy

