Salvage treatment with cystectomy plays an important role in managing patients with chemoradiotherapy and is the gold standard for optimal trimodality therapy should patients relapse. Two approaches here have been reported for patients considered fit for salvage cystectomy. Firstly in the MGH and RTOG protocols, response evaluation is performed after approximately 40Gy of induction therapy [5, 9]. Only complete responders are considered eligible for bladder preservation therapy and proceed with consolidation treatment with the bladder treated up to 64Gy. Conversely, a second alternative is the Erlangen approach [10], where the bladder is evaluated at 4-6 weeks post definitive chemoradiotherapy. The late-response evaluation may theoretically increase the chance of bladder preservation, as some slow responders may still be responding and have not maximally regressed after the 40Gy of treatment. Additionally, split dose radiotherapy is of some concern. However, the two approaches seem equally effective in terms of long term survival and bladder preservation. This study will utilize the latter approach.

An early assessment of efficacy of chemoradiation that is standardly used is the complete response rate, which is determined in most series to be based on first cystoscopic assessment of the bladder cancer 12 weeks after chemoradiotherapy is completed [1, 5]. This involves examination under anesthesia, cystoscopy and biopsy of all previously positive tumor sites that is utilized to evaluate the tumor status (response) following completion chemoradiotherapy. In some patients radiographic or cystoscopic evaluation will reveal abnormalities at the bladder

tumor-site (such as thickening of the wall, ulcerations, or possible nodularities) which contain no identifiable tumor cells histologically. Patients will be considered as having a complete response, or pT0 response, when the bi-manual examination under anesthesia is negative, when all the biopsies are negative for any tumor at the site(s) of the pretreatment tumor(s) and there is an absence of metastatic disease on the most recently performed systemic imaging.

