7.1.2.6.2 Cystoscopic Assessment

Assessment of disease with cystoscopy will take place within 42 days of commencement.

The initial re-evaluation will take place 12 weeks (week 19 of trial) after completing chemoradiotherapy (+/- 7 days) (week 19 of the trial). Evaluation will include urine cytology, rigid cystoscopy, tumour site biopsy if indicated and bimanual examination after TUR.

The second check cystoscopy is mandatory at 24 weeks after completing chemoradiotherapy (+/- 7 days) (week 31 of the trial). Evaluation will include urine cytology, rigid cystoscopy, tumour site biopsy if indicated and bimanual examination after TUR.

In follow up, patients will receive cystoscopic assessment every 3 months for 12 months after week 31, then 6 monthly for 18 months, then 12 monthly until 3 years after the last patient is registered.

Any additional cystoscopic assessment (ie 6 weeks post chemoradiotherapy) is at the clinician discretion.

At the cystoscopic assessments for response (weeks 19 and 31), patients will be determined to have either achieved a Complete Response, Partial Response, Stable Disease or Progressive Disease. The determination will be based upon the results of the urologist assessment of the bladder at cystoscopy, histological parameters and result of most recent systemic imaging, as follows.

Patients will be considered as having a **complete response**, or pT0 response, when: i) the bimanual examination under anesthesia is negative, ii) all the biopsies are negative for any tumor at the site(s) of the pretreatment tumor(s), and iii) there is an absence of metastatic disease on the most recently performed systemic imaging.

Patients will be considered to have a **partial response**, when patients have a lower T stage (depth of invasion of tumour) on tumour biopsy than pretreatment tumour T stage and there is an absence of metastatic disease on the most recently performed systemic imaging.

Patients will be considered to have **stable disease** when patients have the same T stage (depth of invasion of tumour) on tumour biopsy compared to pretreatment tumour T stage and there is an absence of metastatic disease on the most recently performed systemic imaging.

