8.0 STATISTICAL ANALYSIS PLAN

8.1 Statistical Analysis Plan Summary

This is a single arm study. The primary and secondary objectives for the study will be:

Primary

To assess feasibility of pembrolizumab in combination with chemoradiation, as measured by a satisfactorily low rate of unacceptable toxicities (UT's) in the patient sample. A UT is defined as occurrence of any one of the following events:

- a) occurrence of a grade 3 or 4 acute AEs (excluding grade 3 or 4 urinary AE), occurring either during treatment or within 12 weeks after completion of treatment, or

- b) Cisplatin being withheld for \geq 2 doses or any cisplatin dose reductions resulting in <66% of the intended total cisplatin dose being delivered, relative to the cisplatin starting dose.
- c) Radiation treatment being delayed beyond more than 7 weeks
- d) Any pembrolizumab being delayed for more than 6 weeks (Multiple dose delays will not be aggregated).

Patients will be assessed for acute toxicity at each visit throughout treatment and in follow up as outlined in the trial schema. Expected rates of patients experiencing a G3-4 event excluding urinary toxicity having chemoradiotherapy without pembrolizumab are between 5-30% [7, 8, 19]. Grade 3-4 urinary toxicity is a common adverse event experienced during chemoradiotherapy occurring in 20% of patients [12] related to radiation related changes to the bladder resulting in urinary frequency. Rates of urinary toxicity will be collected during the study, but will not contribute to the assessment total of G3-4 events.

The radiotherapy discontinuation rate has been reported to be between 0-5% [7, 8, 19].

The experimental regimen would be worthy of further pursuit if safe and feasible to deliver to patients without excessive toxicity or modification of radiation or dosage of cisplatin.

Secondary

To test for an initial efficacy signal, as measured by the complete response (CR) rate, defined as achieving pT0 at either the 1st or 2nd cystoscopic examination.

Additional secondary objectives are to document (over the 3-5 years of follow up for patients)

- overall survival
- metastatic disease-free survival; and
- locoregional progression free survival

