These goals can be achieved with a sample size of 30 patients. Consider a Simon's two stage design whereby accrual will be halted if we see greater than 5 UT's amongst the first 10 patients and greater than 11 amongst the first 30 patients. Given these stopping thresholds, if the true underlying UT rate is 0.3 then the cumulative probability of concluding unsafe after stage 2 of accrual will be 17% and if the true underlying rate of UT is 0.5 then the cumulative probability of concluding unsafe after stage 2 of accrual will be 90%. The relationship between the true underlying UT rate and the probability of concluding unsafe is shown in Figure 2.

[figure not shown]

Figure 2: Probability of concluding unsafe as a function of true underlying UT rate

As a secondary objective, we desire to test for an initial signal of efficacy by estimating the proportion of patients achieving a best response of complete response (CR). (See sections 3.2 and 7.1.2.6.2 for the definition of best response.) Similar to the procedure for placing thresholds on the number of UT's we define a threshold for the minimum number of CR's that must be seen in the sample in order to consider the regimen worthy of further investigation on the basis of efficacy. We also define a "maximum uninteresting" true underlying CR rate – the true underlying CR rate at or below which we would not consider the regimen clinically worthy of implementation, and a "minimum interesting" true underlying CR rate – the true underlying CR rate at or above which we would consider the regimen clinically worthy of implementation. We define the maximum uninteresting and the minimum uninteresting rates as being 0.5 and 0.7 respectively. If we place the decision threshold at 18 CR's out of 30, then the probability of judging the regimen worthy of further investigation for efficacy if the true underlying CR rate is 0.5 is 10%, and the probability of judging the regimen worthy of further investigation for efficacy if the true underlying CR rate is 0.7 is 84%. This is illustrated in Figure 3.

[figure not shown]

Figure 3: Probability of further investigation as a function of true underlying CR rate.

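### Residual tumour found and resected at the week 19 cystoscopy can be scored as a complete response at week 31, so the CR count can be inflated by resection

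*Combined protocol and SAP*

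**What the plan says.** The first secondary endpoint, in section 3.2, is "Best response, defined as the better of the responses achieved at either the 1st or 2nd cystoscopic examination after completing therapy". Section 8.1 repeats it for CR, "defined as achieving pT0 at either the 1st or 2nd cystoscopic examination", and section 8.2 bases its efficacy decision on the same best response.

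Section 7.1.2.6.2 uses one sentence for both the week 19 and the week 31 examinations: "Evaluation will include urine cytology, rigid cystoscopy, tumour site biopsy if indicated and bimanual examination after TUR". It adds: "The second check cystoscopy is mandatory at 24 weeks after completing chemoradiotherapy". No exception is made for patients with tumour at week 19.

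In the same section CR has three conditions: a negative bimanual examination, negative biopsies at the pretreatment tumour site(s), and no metastatic disease on the latest imaging. Table 8 adds absence of nodal involvement. It scores any new anticancer therapy, including intravesical therapy, as progressive disease. TUR is not named there.

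Other sections describe the assessment without TUR. Sections 4.1.2 and 8.1 list examination under anaesthesia, cystoscopy and biopsy. Figure 1 in section 2.0 marks TURBT only before the study, and the flow chart in section 6.1 has no TUR row.

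**The concern.** None of the CR conditions refers to what was found at the previous examination. A patient scored as partial response or stable disease at week 19 could have the remaining tumour removed at that examination, receive no other new treatment, have negative biopsies at week 31, and enter the analysis as a CR. The surgeon, and not the study regimen, would have produced that response.

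The protocol gives a reason not to assume this is harmless. Section 4.2.4.1 says the pathological complete response rate depends on the extent of the initial TURBT, with 73–79% after a visually complete resection against 50–63% after an incomplete one. A further resection between the two scoring examinations could plausibly matter too.

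At stake is the efficacy rule in section 8.2, where the CR count in 30 patients decides whether the regimen is worth further investigation. Comparison with published rates is also affected, because section 4.1.2 says that CR is "determined in most series to be based on first cystoscopic assessment of the bladder cancer 12 weeks after chemoradiotherapy is completed", which is a single look.

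**Working it through.** **Step 1. Is the route open on the text?** Four conditions are needed.

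- CR at either examination counts: yes (3.2, 8.1, 8.2).
- TUR can occur at the week 19 evaluation: 7.1.2.6.2 mentions it, although other sections do not list it.
- The patient is examined again at week 31: yes, mandatory.
- Nothing bars an upgrade after resection: the only bar is the new-therapy column of Table 8. A TUR done within a protocol evaluation is not clearly a new therapy.

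The route is open. Because the rule takes the better result, it can add CRs but never remove one.

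**Step 2. Reproduce the plan's figures.** From section 8.2: n = 30, threshold 18, CR rates 0.5 and 0.7, stated go probabilities 10% and 84%. Exact binomial:

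- More than 18: P(X ≥ 19) = 0.1002 at 0.5 and 0.8407 at 0.7. These match.
- At least 18: P(X ≥ 18) = 0.1808 and 0.9155. These do not match.

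The stated figures therefore mean more than 18 of 30, and that reading is used below.

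**Step 3. Illustrate the effect.** Let p be the CR rate with no CR created by resection. Let f be the share of week 19 non-CR patients rescored as CR because their tumour was resected. The scored rate is

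s = p + (1 − p) × f.

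The documents give no value for f, so 5% to 30% is an assumption. With p = 0.50, the expected number of rescored patients is 30 × 0.50 × f.

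| f (assumed) | Expected rescored | s | P(go), more than 18 | P(go), at least 18 |
|---|---|---|---|---|
| 0 | 0 | 0.500 | 0.1002 | 0.1808 |
| 5% | 0.75 | 0.525 | 0.1574 | 0.2621 |
| 10% | 1.5 | 0.550 | 0.2327 | 0.3592 |
| 20% | 3 | 0.600 | 0.4311 | 0.5785 |
| 30% | 4.5 | 0.650 | 0.6548 | 0.7802 |

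For example, at f = 10%, s = 0.50 + 0.50 × 0.10 = 0.55. One or two rescored patients on average are enough to more than double the 10%.

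Starting from p = 0.70, f of 5% to 30% gives s of 0.715 to 0.79, and P(go) moves from 0.8407 to between 0.8819 and 0.9860.

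**The case against.** **The null is on the best-of-two scale.** Section 8.2 defines 0.5 and 0.7 as true rates of best response. On that scale the rule still gives a go with probability 10% at 0.5. A reader might infer from the table that the stated 10% is wrong. It is not: the larger figures show how the rule behaves at higher scored rates. They matter only so far as part of the scored rate comes from resection. This objection stands.

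**Some week 31 CRs are genuine.** Section 4.1.2 notes that slow responders may still be regressing at an early look, and pembrolizumab is dosed through week 19. A reader might treat every conversion between weeks 19 and 31 as artefact. The documents do not support that, and f above is confined to conversions caused by resection.

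**The mention of TUR is thin.** The words "tumour site biopsy if indicated and bimanual examination after TUR" may only time the bimanual examination. They do not order resection of residual tumour, and the sections listed above omit TUR. Salvage cystectomy and the Table 8 rule also remove some patients from the route. All this narrows it, and the claim that the CR rate *is* inflated would go too far. It does not close the route, because no section says how a tumour resected at week 19 is scored at week 31.

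**Best-of-two is a deliberate choice**, stated consistently in sections 1.0, 2.0, 3.2, 4.2.4.1, 8.1 and 8.2. A reader might conclude that week 19 CR should replace it as the headline. That would change the endpoint, and the documents do not require it: the decision is against a fixed threshold, not a formal comparison with single-look series.

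**Conclusion.** The gap is real but limited. As written, the plan allows residual tumour resected at week 19 to be scored as CR at week 31. The bias can only be upward, and its size cannot be determined from the documents. Under assumed rescoring shares of 5% to 30%, a rate of 0.50 without such cases would be scored as 0.525 to 0.65, with a 16% to 65% chance of a go instead of 10%. These figures assume a common rescoring share, 30 evaluable patients, and a threshold of more than 18. They do not show that the stated error rate is miscalculated, nor that inflation will occur.

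CR is a secondary endpoint in a pilot whose main decision rests on unacceptable toxicity. The correction is worth making because the CR count has its own decision rule and the remedy is cheap.

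**What to change.** 1. Keep best-of-two as the prespecified endpoint. In sections 3.2, 7.1.2.6.2 and 8.1, add that, for scoring only, a patient whose tumour was found and resected at week 19 remains a non-CR at week 31. This says nothing about whether residual tumour should be resected.
2. In section 8.3, add the CR proportion at week 19 alone, with its Clopper-Pearson interval, as a supportive figure for comparison with series that use the first cystoscopy.
3. Reconcile Figure 1, the section 6.1 flow chart, sections 4.1.2, 7.1.2.6.2 and 8.1, and Table 8 on whether TUR is part of the assessment and whether it counts as new therapy.

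The cost is a few sentences and no new visits, since both cystoscopies and their histology are already part of response assessment. The documents do not show whether the eCRF separates resection from biopsy at week 19, so one data field may be needed. The downside is a slightly lower CR rate, and a genuine late response in a resected patient would not be credited.
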